4.0 STUDY PROCEDURES

4.1 Screening

Recruitment will be conducted via direct communication by the investigator and/or his/her designated staff, advertisement and/or office ads. The Informed Consent discussion and signature process will be conducted by the investigator and/or designated staff. No study-specific assessments will be performed prior to obtaining consent.

A Screen Failure will be defined as a subject who did not meet one or more of the following criteria:

- Did not meet all of the inclusion and/or exclusion criteria
- Did not sign informed consent
- Did not receive a randomization assignment
- Did not undergo at least one procedure (e.g. CellFX or Electrodesiccation)

A screen failure will not be assigned a subject ID and information on this subject will not be entered in the electronic database. Information will be transcribed on the enrollment/screen failure log.

4.2 Subject Selection

4.2.1 Inclusion Criteria

Candidates for this study must meet **ALL** the following criteria:

1. Subject is at least 21 and no older than 80 years of age.
2. Subject has a Fitzpatrick Skin Type I, II, or III.
3. Subject gives voluntary, written informed consent to participate in this clinical investigation and from whom consent has been obtained.
4. Subject must comply with study procedures including follow-up visits.
5. Subject is willing to have SH lesions treated in a single treatment session and understands that their lesion(s) may undergo a second treatment session at a subsequent visit.
6. Subject must have a minimum of four SH lesions and up to 10 SH lesions to be treated and the subject must have at least two SH lesions located on each side of the face.
7. For study purposes, the SH lesions must be no greater than 2 mm in height and must not exceed 5 mm x 5 mm at their largest dimension. The subject's lesions cannot be located within the eye orbit, nose, or scalp.
8. Subject consents to have photographs taken of the SH lesion(s).
9. Subject agrees to refrain from using all other lesion removal products or treatments (e.g. retinols, retinoids, and exfoliating products) to the treated SH lesions or any new SH lesions during the study period.
10. Subject agrees to refrain from prolonged sun exposure during the study period.

4.2.2 Exclusion Criteria

Candidates will be excluded from the study if **ANY** of the following apply:

1. Subject has an implantable electronic medical device.(i.e., pacemaker, implantable cardioverter defibrillator)
2. Subject has an active infection or history of infection in designated test area within 90 days prior to first treatment.
3. Subject is not willing or able to sign the Informed Consent.
4. Subject is known to be immune compromised.
5. Subject is prone to developing hypertrophic scars or to be a keloid producer.
6. Subject has allergies to Lidocaine or Lidocaine-like products.
7. Subject is employed by the sponsor, clinic site, or entity associated with the conduct of the study.
8. Have any condition or situation which, in the Investigator's opinion, puts the subject at significant risk, could confound the study results, or may interfere significantly with the subject's participation in the study.
9. Use of any other investigational drug, therapy, or device within the past 30 days of enrollment or concurrent participation in another research study.

10. Subject was previously treated with CellFX for SH lesions.
11. Subjects with a personal or family history of Muir-Torre Syndrome or with a history of multiple family members with colon cancer
12. Subjects with Basal Cell Nevus Syndrome

4.3 Process for Obtaining Informed Consent

Prior to undergoing any study-specific tests or procedures, the subject must sign and date the site's current and approved Institutional Review Board (IRB) informed consent from in order to be eligible for study participation. The informed consent must contain all elements required by 21 CFR Part 50 and ISO 14155:2011/AC:2011 and comply with the ethical principles of the Declaration of Helsinki.

4.3.1 Process for Obtaining Informed Consent

The patients will be informed by the Investigator or Investigator's designee that they are free to refuse participation in this research study. If they elect to participate, it will be made clear that they may withdraw from the study at any time without prejudicing further care.

The Investigator or the Investigator's designee will inform patients that their medical records will be subject to review by the sponsor or appropriate regulatory bodies. This information will be used during the analysis of the results of the clinical study, but the patients' identities will be treated as confidential. Patients will be assigned a unique study subject code that will not reveal the patients' identity, and this code will be used on all data and data collection forms during the study period. The Investigator will explain the conditions of the study, giving the patient sufficient time to ask questions and to consider whether to participate. Eligible patients who agree to participate will be asked to sign and date an IRB approved informed consent. If the patient agrees, an IRB approved consent form will be provided to the patient for signature and date. One copy shall be returned to the Investigator and filed in the patient's case history; the other copy is for the patient to keep.

4.3.2 Addition of New Information

Pulse Biosciences, Inc. will revise the written informed consent form whenever new information becomes available that may be relevant to the subject's confirmed participation in the study. The revised information will be sent to the Investigator for approval by the IRB. After approval of the IRB, a copy of this information must be provided to the participating subjects, and the informed consent process as described above needs to be repeated. Please follow the central IRB guidelines on the process of re-consenting subjects.

4.4 Schedule of Events and Evaluations

Schedule of events and evaluations required for this study are provided in **Table 2**.

Table 2. Schedule of Events

Study Activity/ Procedure	Visit 1 Enrollment 1 st TX	Visit 2 7-days after 1 st TX	Visit 3 30-days after 1 st TX	Visit 4 60-days after 1 st TX	Visit 5* 90-days after 1 st TX
	Day -0	Visit Range ±3 days	Visit Range ±7 days	Visit Range ±7 days	Visit Range ±7 days
Informed Consent	✓				
Demographics, Medical HX, Fitzpatrick Skin Type	✓				
Randomization	✓				
1 st TX (CellFX + Electrodesiccation)	✓				
2 nd TX (CellFX and/or Electrodesiccation)			✓ If applicable		
Photographs of pre and post treated SH Lesions	✓	✓	✓	✓	✓
Wound Healing Characteristics	✓	✓	✓	✓	✓
Lesion Clearance Assessment			✓	✓	✓
Pain Score/Assessment for muscle twitching: Treated SH Lesions	✓		✓		
5 Point Investigator and Subject Global-Aesthetic Improvement Scale (GAIS)**			✓ ***	✓	✓
6 Point Subject Satisfaction Scale (SSS)/ 5 Point Recommendation Scale**				✓	✓
Adverse Event Assessment	✓	✓	✓	✓	✓
Study Exit				✓	✓

*The 90-day visit is only for subjects that received a second treatment at the 30-day visit.

** The three scales (GAIS, SSS, and 5-point recommendation scale) are completed one time by the subject (e.g., 60 days post last treatment).

***The GAIS is performed by the blinded site investigator at 30-days and 60-day post last treatment.

4.5 Screening / Enrollment Procedures

The following evaluations are required at the time of the subject screening/baseline visit.

4.5.1 Activities prior to or on same day as study enrollment

- Evaluation for Inclusion/Exclusion criteria.
- Collect Demographic information and medical history including but not limited to age, gender, race, ethnicity, dermatologic conditions, and Fitzpatrick skin type.
- Sign the consent form prior to any study activities.
- Receive a copy of the signed consent form.

4.5.2 Definition of Enrollment

Once the subject has been consented, randomized, and has received a CellFX and Electrodesiccation treatment, the subject will be considered enrolled and each enrolled subject will be assigned a unique Study Identification Number.

4.5.3 CellFX Treatment / Electrodesiccation Treatment

- Up to 10 clinically diagnosed SH lesions that meet the study criteria will be selected by the treating investigator and prior to assigning lesions the subjects should have baseline photos taken.
- The site will log onto the Captivate EDC system. The randomization assignment will include the type of treatment and which side of the face for CellFX and Electrodesiccation.
- A template may be used to determine which treatment tip size will be used for each lesion – sizes range between 1.5 mm x 1.5 mm and 5.0 mm x 5.0 mm. The identified lesions will be numerically labeled.
- The blinded site investigator will then perform a baseline lesion(s) assessment.
- Photographic images of each selected lesion will be taken prior to using local anesthesia/numbing.
- Local anesthesia/numbing will be applied to all selected study lesions.
- Each lesion randomized to CellFX will be treated with pre-determined energy settings; each lesion randomized to Electrodesiccation will be treated as defined in **Section 3.5**.
- The subject will be asked to rate his/her pain immediately after each lesion treated with the CellFX and Electrodesiccation procedures by using a numerical rating score.
- The subjects will be asked whether they felt muscle twitching immediately after each lesion treated with CellFX.
- Post procedure lesion assessment will be performed by the blinded site investigator.
- Photographic images of each selected lesion will also be taken post-treatment.
- A light bandage and/or any physician recommended dressing may be applied before the subject leaves the clinic.
- Any adverse events will be identified and documented.

4.6. 7-Day Follow-up Visit

- Photographic images of each of the study lesions will be taken with pre and post lesion markings.
- All lesions will be clinically assessed by the blinded site investigator.
- Any adverse events will be identified and documented.

4.7 30-Day Follow-up Visit (Optional CellFX/Electrodesiccation Treatment #2)

- Photographic images of each of the study lesions will be taken with pre- and postlesion markings.
- All lesions will be clinically assessed by the blinded site investigator and rated using GAIS scale and the 4-point lesion clearance scale.
- If any lesion is rated 1-4 on the GAIS scale, a second treatment with CellFX or electrodesiccation will be performed to the previously treated lesion.

In case of a second CellFX or Electrodesiccation treatment:

- Local anesthesia/numbing will be applied to each lesion designated for retreatment.
- Each lesion designated for a CellFX retreatment will be treated using pre-determined energy settings.
- Each lesion designated for Electrodesiccation retreatment will be performed as outlined in protocol **Section 3.5**.
- The subject will be asked to rate his/her pain immediately after each lesion treated with CellFX and/or Electrodesiccation treatments by using a numerical rating score.
- The subjects will be asked whether they felt muscle twitching immediately after each lesion treated with CellFX.
- Post procedure lesion assessment will be performed by the blinded site investigator.
- Photographic images of the retreated lesions will also be taken post-treatment.
- A light bandage and/or any physician recommended dressing may be applied before the subject leaves the clinic.
- Any adverse events will be identified and documented.

4.8 60-Day Follow-up Visit

- **This is Final Study visit for any subject for whom all lesions were treated only one time.**
- Photographic images of each of the study lesions will be taken with pre and post lesion markings.
- All lesions will be clinically assessed by the blinded site investigator and rated using the GAIS scale and the 4- point lesion clearance scale.
- 5-point Investigator-and-Subject-Global-Aesthetic-Improvement-Scale
- 6-point subject satisfaction scale
- 5-point subject scale related to recommendation of procedure(s)
- Any adverse events will be identified and documented.

4.9 90-Day Follow-up Visit

- **This is Final Study visit for any subject for whom lesion(s) were retreated at the 30-day follow-up.**
- Photographic images of each of the study lesions will be taken with pre and post lesion markings.
- All lesions will be clinically assessed by the blinded site investigator and rated using the GAIS scale and the 4-point lesion clearance scale.
- 5-point Investigator-and-Subject-Global-Aesthetic-Improvement-Scale
- 6-point subject satisfaction scale

- 5-point subject scale related to recommendation of procedure(s)
- Any adverse events will be identified and documented.

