3.0 PROTOCOL

3.1 Study Objectives

The primary objective of this study is to compare the safety and effectiveness of the CellFX System to Electrodesiccation (Hyfrecator electrosurgical unit) performed with a non-insulated needle-shaped electrode for removal and treatment of SH lesions in healthy adult subjects.

The following objectives are to evaluate the overall response to CellFX and Electrodesiccation:

- SH lesion response after treatment vs. the pre-treated appearance of the same lesion
- SH lesion response at various points in time over several weeks following the initial treatments vs. the same pre-treated lesion
- Document the condition of skin in the treatment areas (erythema, swelling, crusting, hyperpigmentation, hypopigmentation, etc.) over the course of various time periods post-initial CellFX and Electrodesiccation treatment, and
- Document all safety related issues that may be considered as adverse side effects or serious adverse events

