3.2 Study Design

This study is designed as a multicenter, single-blinded, prospective, randomized, comparison IDE study between CellFX System and Electrodesiccation.

The Principal Investigator will select a sub investigator to be the blinded investigator to classify the healing characteristics and aesthetic appearance of each subject's selected lesions at baseline and treated lesions post treatment and at 7-days, 30-days, and 60-days following the last CellFX

treatment or Electrodesiccation. This sub investigator will be blinded to the treatment assignment. The subject may not be blinded to the treatment assignment.

Eligible subjects with a minimum of 4 and up to 10 SH lesions meeting the inclusion and exclusion criteria will be enrolled. The SH lesions may be present anywhere on the face except the scalp, nose and within the orbital region of the face. The subject must have at least two SH lesions on each side of the face. Subjects will be randomized to receiving the two treatments in a split-face design with CellFX being used on only one side of the face and Electrodesiccation on the other side. A minimum of two lesions must be treated with CellFX and a minimum of two lesions must be treated with Electrodesiccation per subject. Selected lesions for each treatment modality must be clearly separated in distance from each other so that lesion treatment and side effects can be assessed by the blinded site investigator.

All selected and qualifying study lesions will receive at least one CellFX or Electrodesiccation treatment. Each subject will be evaluated by the blinded site investigator at 7-days, 30-days, and 60-days post-initial CellFX and Electrodesiccation treatments. At the 30-day follow-up visit, if any lesion is rated 1-4 on the Global Aesthetic Improvement Scale (GAIS), the lesion must receive an additional treatment. In case of a second treatment, the subject will be evaluated by the blinded site investigator at 30-days and 60-days post-retreatment. Photography of the study lesions will be captured along with the blinded site investigator assessments at all visits.

Note:

Eligible lesions that should be treated and do not receive a retreatment will be considered a protocol deviation. The reason(s) for not receiving an additional treatment will be collected on the electronic case report form (eCRF). These subjects will remain in the study and will be included in the ITT population.

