3.7 Number of Subjects

Up to 60 subjects at up to 5 sites will be enrolled.

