9.0 ADVERSE EVENTS

Pulse Biosciences will classify each reported Adverse Event according to ISO 14155:2011. All protocol specific AEs, whether device-related or not, will be recorded on the AE case report form and reported. Data to be collected will include the description of the AE, onset, and resolution dates (or whether the AE is ongoing), severity, management/treatment, outcome, and determination of the relationship to the device and/or procedure. All AEs related to the lesion site(s) should be reported and classified by the blinded site Investigator and to be followed by the treating Investigator to determine the relationship of the AE to the device or the study procedure.

All AE information will be collected from enrollment through 60 days following the last CellFX and Electrodesiccation procedures. All AEs will be followed until the event has resolved (in the case of permanent impairment, the event will be followed until it stabilizes, and the overall clinical outcome has been ascertained).

When reporting AEs/SAEs, the Investigator should include the following information:

- Description of event
- Onset of event
- Duration of event
- Severity
- Relationship to device or procedure
- Action taken
- Subject outcome

Severity describes the intensity of an event and will be assessed as:

- **Mild:** The AE does not interfere in a significant manner with the subject's normal functioning level.
- **Moderate:** The AE produces some impairment of function but not hazardous to health.
- **Severe:** The AE produces significant impairment of function or incapacities and/or it is a hazard to the subject.

Relationship to device or procedure will be assessed as:

- **Unlikely:** There is no indication that the AE was caused by the investigational or standard of care device.
- **Possibly:** It cannot be excluded that the AE was caused by the investigational or standard of care device.
- **Likely:** A causal relationship between the investigational or standard of care device and the AE is at least a reasonable possibility; i.e. there is evidence or argument suggesting a causal relationship.

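### The blinded evaluator examines lesions immediately after each procedure: an avoidable exposure that could disclose the treated side to the only named rater of both co-primary safety endpoints

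*Combined protocol and SAP*

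**What the plan says.** Section 3.2 sets up the rater: "The Principal Investigator will select a sub investigator to be the blinded investigator". That person is to be blinded to assignment and rates lesions at baseline, then "treated lesions post treatment and at 7-days, 30-days, and 60-days following the last CellFX" treatment or electrodesiccation. Section 4.5.3 lists the steps on the day of treatment. After the procedures and the pain and twitching questions, and before any dressing, it says: "Post procedure lesion assessment will be performed by the blinded site investigator". Section 4.7 has the same step after a retreatment. Table 2 (Section 4.4) carries "Wound Healing Characteristics" at Visit 1, and Section 9.0 adds: "All AEs related to the lesion site(s) should be reported and classified by the blinded site Investigator".

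Section 6.1.1 defines both co-primary safety endpoints as judged by the blinded site investigator: pigment change or scarring at 60 days, and skin texture change at 30 days, after last treatment. It names no other rater. Sections 3.2 and 4.7 use this rater's 30-day GAIS to decide on retreatment. The effectiveness co-primary (Section 6.1.2) is scored by three independent observers from photographs at baseline and 60 days after last treatment.

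**The concern.** The two safety co-primaries are present/absent judgements with no independent reader, so they depend on this one rater's blinding. The plan has that rater look at the treated skin when traces of the procedure are freshest, once on Day 0 and again for anyone retreated. It describes no masking for the step.

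A rater who learned the side might under-call events on the CellFX side, which favours a false finding of non-inferiority, or over-call them, which costs power. The documents give no reason to expect one direction. The 30-day retreatment decision is exposed in the same way.

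**Working it through.** **1. Could the immediate look disclose the side?** The documents do not describe or compare the immediate appearances. Three things make disclosure plausible:
- CellFX uses a non-thermal surface tip of 1.5 x 1.5 mm to 5.0 x 5.0 mm (Sections 1.5, 3.4). The comparator is a needle electrode that heats and desiccates the lesion (Section 2.3).
- The Table 1 footnote relies on a photograph taken straight after CellFX to confirm a mistargeted lesion, so some trace of the application site is expected to be visible then.
- Each device is confined to one side of the face (Section 3.3), so recognising one lesion identifies the side for all of them.

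**2. Could the rater remember it 30 to 60 days later?** "Up to 60 subjects at up to 5 sites will be enrolled". If five sites enrol equally with one rater each, 60/5 = 12 subjects per rater. Recall is feasible, not certain.

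**3. Is the immediate rating needed from this rater?** The wound-healing endpoints in Section 6.2 are at 7, 30 and 60 days. No primary, secondary or exploratory endpoint uses the same-day rating. It does serve the Section 3.1 objective to "Document the condition of skin in the treatment areas" over time, so it should be reassigned, not dropped.

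**4. Size of a rater bias, as illustration.** From the plan: margin 15 points, one-sided 2.5%, target 260 lesions, hence 260/2 = 130 per arm. Assumed, because the plan gives no values: comparator event rate pE of 5% to 30%, within-subject correlation rho of 0 or 0.5, and a shift b of 2 or 4 points in the recorded CellFX rate pC.

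SE = sqrt((1 - rho) x (pC(1 - pC) + pE(1 - pE)) / 130)

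*Under-calling with the true difference at the margin.* pC = pE + 0.15 - b; type I error = Phi(b/SE - 1.96). Example, pE = 0.20, rho = 0, b = 0.04: pC = 0.31, SE = sqrt((0.2139 + 0.16)/130) = 0.0536, and Phi(0.746 - 1.96) = 11.2%.

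| pE | rho | b = 0 | b = 2 points | b = 4 points |
|---|---|---|---|---|
| 5% | 0 | 2.5% | 7.4% | 18.7% |
| 5% | 0.5 | 2.5% | 10.9% | 32.7% |
| 10% | 0 | 2.5% | 6.4% | 14.5% |
| 10% | 0.5 | 2.5% | 9.1% | 24.7% |
| 20% | 0 | 2.5% | 5.6% | 11.2% |
| 20% | 0.5 | 2.5% | 7.5% | 18.3% |
| 30% | 0 | 2.5% | 5.2% | 10.0% |
| 30% | 0.5 | 2.5% | 6.9% | 15.9% |

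*Over-calling with equal true rates.* pC = pE + b; power = Phi((0.15 - b)/SE - 1.96). Example, pE = 0.20, rho = 0, b = 0.04: pC = 0.24, SE = sqrt((0.1824 + 0.16)/130) = 0.0513, and Phi(2.144 - 1.96) = 57%.

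| pE | rho 0: b = 0 to 4 points | rho 0.5: b = 0 to 4 points |
|---|---|---|
| 5% | >99% to 94% | >99% to >99% |
| 10% | 98% to 78% | >99% to 97% |
| 20% | 86% to 57% | 99% to 86% |
| 30% | 75% to 48% | 96% to 77% |

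*How many lesions is that?* Of 130 CellFX lesions, 2 or 4 points is 2.6 or 5.2. At pE = 20% the events expected at the margin are 0.35 x 130 = 45.5, so the shift is 6% or 11% of them. At pE = 5% they are 0.20 x 130 = 26, and it is 10% or 20%. The largest type I figures therefore need the largest relative misclassification.

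*Two qualifications.* All three co-primaries must succeed (Section 6.1.3), so the type I figures are upper bounds on false study success. Section 6.1.1 also says the difference should not exceed 7.5%. If that is a condition on the point estimate, type I error becomes Phi((c - 0.15 + b)/SE), where c is the smaller of 0.075 and 0.15 - 1.96 x SE. At pE = 5%, rho = 0.5, b = 0.04, SE = 0.0265 and Phi(-0.035/0.0265) = 9.3% in place of 32.7%. Across the same grid the ranges become about 2-8% for 2 points and 9-18% for 4 points.

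**The case against.** The strongest case against is that harm from this step is inferred. Device mechanism is not surface appearance. The Table 1 footnote concerns CellFX alone and does not show that its sites look different from electrodesiccated ones. The same local anaesthetic is used on both sides (Sections 3.5, 4.5.3) and could obscure early differences. All of this stands, and it is why disclosure is called plausible and no more.

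Second, the rater has other clues. The same person scores healing on Day 7, and "The subject may not be blinded to the treatment assignment". This also stands. The tables therefore show what any rater bias of 2 or 4 points would do, and the increment from the immediate look cannot be separated out. The difference is that the Day-7 rating serves a listed endpoint and the immediate one serves none, so removing the latter loses no endpoint data.

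Third, Section 9.0 gives lesion-site adverse events to the blinded investigator, and moving same-day ones to the operator gives up some blinding. That is a real cost, limited to events that first appear after that day's procedure.

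A reader might infer that the blind is in fact broken, that the trial's type I error is inflated by the amounts above, or that the plan favours CellFX. The documents support none of these: they give no appearance data, no safety event rates for this design and no direction of bias. Nor is the effectiveness rating directly exposed. Only an indirect route through retreatment decisions remains.

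**Conclusion.** The point holds as an avoidable risk to blinding, not as a demonstrated failure of it. The text is clear that one role does the immediate assessments, rates both safety co-primaries alone and triggers retreatment. That this discloses the side rests on inference from the devices, the photograph footnote and the one-side-per-device allocation. Bias would further require the rater to remember the side and rate differently because of it.

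If it did, a shift of a few lesions would be enough to move type I error or power materially, within the ranges shown and subject to their assumed inputs. The share of any such shift due to this step is unknown. This is a cheap improvement of modest, unquantified benefit.

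**What to change.** - **Sections 3.2, 4.5.3 and 4.7, and the same-day post-procedure entries in Table 2 (Visit 1, and Visit 3 if retreated):** assign the immediate post-procedure assessment to the treating investigator.
- **Blinded evaluator:** completes all of that day's ratings before any treatment, then does not see the lesions again that day. Day-7, Day-30 (before any retreatment), Day-60 and Day-90 ratings stay as planned.
- **Photographs:** the evaluator does not see the immediate post-procedure images at any time before that subject's final rating. Any check of them for mistargeting is done by the treating investigator after the blinded Day-30 ratings are recorded. Baseline photographs, which Section 6.2 gives as the aid for the in-person GAIS, remain available.
- **Section 9.0:** lesion-site adverse events that first appear after that day's procedure are recorded and classified by the treating investigator. All others, including those found at the Day-30 examination before retreatment, stay with the blinded evaluator.

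The cost is wording changes, with no extra visits or staff. The downside is that the same-day wound description and the classification of new same-day lesion events become unblinded. Some risk remains, since Day-7 healing and remarks from unblinded subjects may still give clues.
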